6.3 RANDOMIZATION AND BLINDING

Eligible women will be randomized in a 1:1 ratio to the therapeutic yoga or physical conditioning interventions, with stratification by study site. The randomization scheme will be generated by a computer algorithm using randomly permuted blocks of sizes of 2 and 4. To avoid manipulation of randomization, a statistician/analyst who is not otherwise involved in the study will prepare the randomization scheme.

When a participant is found to be eligible and willing to be randomized at the Baseline Visit, the coordinator will confirm appropriateness for randomization on the randomization assignment form in the Medrio electronic data capture system. The system will provide a randomization number corresponding to the participant's intervention assignment, consistent with the randomization scheme. Sequential randomization numbers will provide a check on the validity of randomization, and the system will be configured to prevent reversal or manipulation of randomization.

Although there is no effective way to completely blind participants in this trial to their intervention assignment, study procedures will preserve the blinding of investigators and staff involved in abstracting or analyzing outcomes. Only study personnel who are directly responsible for randomizing participants, administering interventions, or promoting adherence to interventions will be aware of intervention assignment. All personnel involved in abstracting, assessing, or analyzing pain-related outcomes will remain blinded until all participants have completed the final visit, trial data are edited and cleaned, and the dataset is locked.

The Medrio electronic data capture system will be programmed to hide information about intervention assignment from study investigators or staff who are required to remain blinded. Only study personnel who are required to remain unblinded will be given user rights in the Medrio system that allow them to view the intervention assignments for individual participants.

To minimize differential expectations of success between groups, participants will be told that they are participating in a study of two types of low-impact physical activity programs and that the investigators do not know which intervention is more effective for the management of chronic pelvic pain (which is true). While awareness of group

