9.2 SAMPLE SIZE DETERMINATION

In this pilot randomized trial is designed to assess the feasibility of and field-test procedures for a future full-scale randomized efficacy trial, a sample size of 36 participants has been selected based on consideration of the study goals as well as the time and budget constraints of the R34 funding mechanism. This pilot sample size allows for group intervention classes with an average size of 6 participants per class to be assembled for each intervention group at each of the three proposed study locations, consistent with expectations for a possible future full-scale randomized trial.

In the overall sample of 36 women, margins of sampling error (MSEs; i.e., half-widths of 95% CIs) for continuous and binary feasibility measures will be greater than 0.30 SDs and up to 15 percentage points, respectively, with the latter depending on the true proportion. Within arms, corresponding MSEs will be greater than 0.45 SDs and 20 percentage points. Given the substantial MSEs, the investigative team will take into account uncertainty about parameter estimates when drawing study conclusions.

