9.4.5 PRIMARY COMPOSITE FEASIBILITY OUTCOME

Although each of the above feasibility analyses will be important in planning for a future full-scale efficacy trial, the investigative team has also designated a single composite feasibility outcome that incorporates multiple of the above outcomes. This is the cumulative number of participants from all three planned intervention waves who:

- a) are randomized to one of the two intervention groups (yoga or physical conditioning),
- b) do not drop out of the study before the end of their assigned 8-week intervention program,
- c) attend at least 75% of their recommended group intervention classes over 8 weeks,
- d) report at least moderate self-efficacy (on average) in performing intervention techniques, and
- e) provide 7-day pain severity/intensity, impact, and interference data at 8 weeks.

The investigative team has set a benchmark of enrolling and following at least 24 women (or two-thirds of the randomization target of 36 women) who meet all of the above criteria by the end of three planned intervention waves of this feasibility trial. If this benchmark is not met, the study team will re-consider the advisability of proceeding with a full-scale trial that uses the same approach to recruitment and retention, delivering the study interventions, and collecting pain outcomes data.

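### Section 9.2 puts the 95% half-width for a binary measure in 36 women at no more than 15 percentage points; the maximum is 15.5 to 17.1, depending on the interval method.

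*Combined protocol and SAP*

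**What the plan says.** Section 9.2 states that "a sample size of 36 participants has been selected", on grounds of study goals, time and budget. It then describes precision through "margins of sampling error (MSEs; i.e., half-widths of 95% CIs". For the overall sample, the half-widths, with continuous measures listed first and binary ones second, "will be greater than 0.30 SDs and up to 15 percentage points, respectively, with the latter depending on the true proportion". For the separate arms it adds: "Within arms, corresponding MSEs will be greater than 0.45 SDs and 20 percentage points". Section 6.3 gives the allocation ("Eligible women will be randomized in a 1:1 ratio"), which implies 18 women per arm.

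The section names no interval method and does not restrict the range of proportions. It describes the margins as substantial and undertakes to allow for uncertainty when conclusions are drawn.

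**The concern.** Three of the four figures in the paragraph are worded as lower bounds, where rounding down is harmless. The overall binary figure is worded as an upper bound, where rounding down makes the statement untrue. With 36 women, the familiar calculation at a proportion of one half gives more than 16 points, so the bound of 15 looked too low.

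What is at stake is limited. Section 9.2 is the plan's only statement of how precisely binary feasibility measures will be estimated, and sections 9.4.2 to 9.4.4 allow 95% CIs to be reported to guide planning of the full-scale trial. A reported interval could be wider than the plan says is possible.

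**Working it through.** **Inputs.** n = 36 overall (section 9.2). Two-sided 95% level, z = 1.96 (section 9.2). The proportion is not fixed ("with the latter depending on the true proportion"), so the bound has to hold at the least favourable value. n = 18 per arm (36 split 1:1, section 6.3).

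**The plan's other figures first.** For a continuous measure the half-width in SD units is z/√n.

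- n = 36: 1.96/6 = 0.327 (0.338 with a t quantile), against a stated lower bound of 0.30.
- n = 18: 1.96/√18 = 0.462 (0.497 with t), against a stated lower bound of 0.45.

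Both agree with the text. The overall binary figure does not reproduce, as shown next.

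**Maximum binary half-width, n = 36.**

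- Wald: z√(p(1−p)/n), largest at p = 0.5: 1.96 × 0.5/6 = 0.1633, or 16.3 points.
- Wilson: at p = 0.5 the formula reduces to 0.5z/√(n + z²) = 0.98/√(36 + 3.84) = 0.98/6.312 = 0.1553, or 15.5 points.
- Jeffreys and Clopper-Pearson: computed for every count from 0 to 36 and maximised.

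| Method | Maximum (at 18/36) | Counts with half-width above 15 | At 24/36 | Smallest n with maximum ≤ 15 |
|---|---|---|---|---|
| Wilson | 15.5 | 14 to 22 | 14.7 | 39 |
| Jeffreys | 15.8 | 13 to 23 | 14.9 | 41 |
| Wald | 16.3 | 11 to 25 | 15.4 | 43 |
| Exact | 17.1 | 9 to 27 | 16.2 | 47 |

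Agresti-Coull has the same maximum as Wilson (15.5). Mid-P gives 16.0 and continuity-corrected Wald 17.7.

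The Wald sample size follows from 0.25 × (1.96/0.15)² = 42.7, rounded up to 43. A different confidence level does not explain the figure: a 90% Wald interval has a maximum of 13.7.

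**Where the stated bound holds.** The Wald half-width is 15 or less when the true proportion is at most about 0.30 or at least about 0.70. It is 14.1 at 75%, 11.7 at 85% and 9.8 at 90%.

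**Within arms, n = 18.** The maximum, at 9/18, is 21.0 (Wilson), 21.6 (Jeffreys), 23.1 (Wald: 1.96 × 0.5/√18) or 24.0 (exact). All exceed 20, so the within-arm figure is consistent with the text if it is read as a statement about the maximum.

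**The case against.** The strongest reply is that this is rounding. All four figures in the paragraph are round numbers given for orientation, no interval method is named, and the text itself says the binary figure varies with the proportion. The smallest maximum is only half a point above 15. This fairly describes the size of the error but does not remove it: even 15.53 rounds to 16, and an upper bound cannot safely be rounded down.

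The second reply is that most benchmarks lie where 15 holds: drop-out of 15 to 25%, adherence of 75 to 85%, self-efficacy and competence above 75%, data return above 90%. The one 50% benchmark, the share of screened women who are randomized, has screenees as its denominator, so n is larger than 36. The only benchmark for the 36 women in the affected range is the composite in section 9.4.5 ("at least 24 women (or two-thirds of the randomization target of 36 women"). There the answer depends on the method: Wilson and Jeffreys stay just under 15, while Wald and exact exceed it. That benchmark is a count and uses no interval. All of this stands and limits the importance. It does not make the sentence correct, because the sentence covers binary feasibility measures in general, and observed proportions could fall mid-range if feasibility proves poor.

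Third, nothing downstream depends on the figure: 36 was not chosen for precision, and CIs are optional. That also stands, and it is why the point is minor.

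**Conclusion.** The stated ceiling is wrong as written. With 36 women, none of the standard two-sided 95% methods checked keeps the half-width for a binary measure at or below 15 points across all proportions. The understatement is 0.5 points (Wilson) to 2.1 points (exact), confined to mid-range proportions. This rests on taking the phrase as a maximum over the true proportion and on all 36 women contributing; with fewer, the half-widths would be larger.

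The within-arm sentence is not counted as an error. It states a floor where the overall sentence states a ceiling, so the two figures cannot be compared directly. A literal floor of 20 could not hold at every proportion either: Wald at n = 18 gives 16.5 at 85% and 13.9 at 90%. That is a reason to put both on the same footing. Confidence in the arithmetic is high; the practical weight is low.

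**What to change.** In section 9.2, give the overall binary figure as up to about 16 percentage points (17 with exact intervals) in all 36 women. For consistency, give the within-arm figure as a maximum too: up to about 23 percentage points (24 with exact intervals) in 18 women. State that both are smaller for more extreme proportions.

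The word "about" should stay, since the unrounded Wald maxima are 16.33 and 23.10 and the exact maximum for 36 women is 17.08. The cost is the wording of two sentences; sample size, design, benchmarks and analyses are unchanged.

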9.3 POPULATIONS FOR ANALYSES

Selection of participants for inclusion in analyses will depend on the endpoints involved. Specifically:

- Analyses addressing the feasibility of recruitment will focus on the total number of women responding to recruitment advertisements, as well as the smaller subset of women who provide informed consent at the Screening Visit.
- Analyses addressing the feasibility of retention in the 8-week intervention period will focus on participants who are randomized to an intervention group, even if these participants do not go on to complete recommended intervention sessions.

Analyses of the feasibility of retention in the post-intervention follow-up phase will focus on participants who complete the 8-week intervention programs.

- Analyses addressing adherence to study intervention classes and home practice will focus on the subpopulation of participants who complete their 8-week intervention programs. In the case of adherence to post-intervention practice, analyses will focus on the subpopulation of participants who complete the additional post-intervention follow-up period.
- Analyses addressing the feasibility of teaching participants to practice intervention techniques will focus on participants who: 1) are randomized to one of the two intervention programs, and 2) do not withdraw early from their assigned 8-week intervention program. Participants will be included in analyses even if they miss one or more intervention classes or do not complete home intervention practice.
- Analyses addressing completeness of pain measure outcomes data will focus on participants who are randomized to an intervention group and who complete: a) the 8-week intervention portion of the study (for assessment of completeness of 8-week pain outcomes data), and b) the 8-week post-intervention follow-up visit (for assessment of 8-week post-intervention follow-up pain outcomes data).

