In this pilot study, all women who participate in at least one intervention session (including the orientation session) will be considered to have been exposed to the intervention and will be included in analyses of study retention. Women who participate in at least one intervention session and complete the 8-week study follow-up visit at the end of the intervention program will be included in analyses of adherence to study intervention classes and home practice sessions.

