4.4 END-OF-STUDY DEFINITION

In this trial, participants will be considered to have completed the intervention phase of the study if they have been randomized, have attended at least one intervention session, and have completed the 8-week follow-up visit. Participants will be considered to have completed the post-intervention portion of the study if they additionally complete the 8-week post-intervention visit. The end of the overall study is defined as completion of the 8-week post-intervention assessment as shown in the Schedule of Activities (SoA), Section 1.3.

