7 STUDY INTERVENTION DISCONTINUATION AND PARTICIPANT WITHDRAWAL

7.1 DISCONTINUATION OF STUDY INTERVENTIONS

Participants may discontinue participation in study interventions at any time, although the investigative team will strive to minimize early discontinuation except when necessary for participant safety. Investigators may also discontinue a participant's involvement in study interventions for the following reasons:

- Continued participation would not be in the best interest of the participant or might require an additional treatment that would confound interpretation of the study data
- Disruptive behavior by a study participant that interferes with the conduct of study intervention classes
- New development or discovery of a study exclusion criterion that precludes further study participation

When a participant discontinues her participation in study yoga or physical conditioning classes or home practice but does not withdraw from the overall study, attempts will be made to complete remaining study procedures as indicated by the study protocol. At the time of intervention discontinuation, the study team will document:

- The reason(s) for discontinuing participation in study interventions,
- Whether the participant is expected to continue study follow-up assessments

If the reasons for discontinuation of study interventions is an Adverse Event (AE) or Serious Adverse Event (SAE), or unanticipated problem, study staff will collect information about the AE/SAE or unanticipated problem and document that this is the cause of study intervention participation (see sections 8.3 and 8.4).

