9.4 STATISTICAL ANALYSES

9.4.1 GENERAL APPROACH

For descriptive statistics, categorical variables will be presented as frequency counts and percentages. Continuous variables will be presented as means and standard deviations. If on visual inspection of q-q plots, distributions deviate significantly from normality continuous variables will also present median and interquartile range.

Where needed, inferential statistics will be generated using Chi-square tests, Fisher's exact tests, or t-tests as appropriate. If outcome variable distributions deviate significantly from normality then comparisons will be made using the Mann-Whitney U test .

9.4.2 MAIN ANALYSES TO ADDRESS AIM 1

Analyses to assess the feasibility of participant recruitment, retention, and adherence to interventions will use data obtained from study visit and randomization logs, intervention class attendance logs, and home intervention practice logs, primarily during the baseline and 8-week intervention period.

Feasibility of recruitment will be assessed by examining the proportion of participants who attend a Screening Visit who go on to be randomized ("Percentage of screenees who are eventually randomized").

Feasibility of participant retention during the intervention phase of the research will be assessed by examining the proportion of randomized participants in each intervention

arm who drop out before the 8-week visit ("Percentage of randomized participants who drop out by 8 weeks, by intervention arm").

Feasibility of promoting participant adherence to group intervention classes will be assessed by examining the percentage of non-dropout participants in each intervention arm who complete at least 75% of recommended group classes during the 8-week intervention period ("Percentage of non-drop-outs completing at least 75% of intervention classes over 8 weeks, by intervention arm").

Feasibility of promoting adherence to home intervention practice will be assessed by examining the percentage of non-dropout participants in each arm who complete at least 75% of recommended home practice hours during the 8-week intervention period ("Percentage of non-drop-outs completing at least 75% of home intervention practice over 8 weeks, by intervention arm").

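### Read literally, section 9.3 can drop women who stop classes but attend the 8-week visit from the Aim 2 (teaching) rates, which may make those rates too favourable

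*Combined protocol and SAP*

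**What the plan says.** **Aim 2.** Section 9.3 admits to the teaching analyses randomized women who "do not withdraw early from their assigned 8-week intervention program". Its next sentence keeps women who only miss classes or home practice. Section 9.4.3 takes as denominator the women completing the program, for self-efficacy and for observed competence alike. It expects over 75% in each case to be at least moderate (for yoga, an average rating of 3 or higher).

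**Stopping classes versus leaving the study.** Section 7.1 covers a woman who gives up classes or home practice without leaving the study. For her, "attempts will be made to complete remaining study procedures as indicated by the study protocol". Withdrawal from the study is handled separately in 7.2.

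**Adherence.** Section 9.3 says these analyses "will focus on the subpopulation of participants who complete their 8-week intervention programs". Section 4.3 puts into the adherence analyses "Women who participate in at least one intervention session and complete the 8-week study follow-up visit at the end of the intervention program". Section 4.4 counts the intervention phase as completed by randomized women who "have attended at least one intervention session, and have completed the 8-week follow-up visit". Section 9.4.2 uses "the percentage of non-dropout participants in each intervention arm who complete at least 75% of recommended group classes", and its drop-outs are the women in each "arm who drop out before the 8-week visit".

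**Composite.** Section 9.4.5, criterion b, refers to dropping out of the study, not of the program. The benchmark is a count of at least 24 women.

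**The concern.** Call a woman who stops classes but stays in the study and attends the 8-week visit a stopper. The plan foresees her, and the schedule in 1.3 and the visit list in 8.1 call for her self-efficacy questionnaire at 8 weeks. Yet the Aim 2 rule in 9.3 turns on leaving the program, so an analyst who applies it as written would set her data aside.

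Some women may leave because they could not manage the postures or exercises, and these are failures that a measure of teaching feasibility should count. Removing them would raise the self-efficacy and competence percentages. Those percentages are compared with an expectation of over 75%, and under 9.4.9 they are examined after the first and second waves to refine procedures.

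**Working it through.** The plan gives no expected number of stoppers and no figure that depends on them, so there is nothing to reproduce. The check has two parts.

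**1. Where a stopper falls under each text**

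| Text | Rule | Is the stopper included? |
|---|---|---|
| 9.3, Aim 2 | No early withdrawal from the program | No, if leaving classes is withdrawal from the program |
| 9.4.3, Aim 2 | Completing the program | Unclear; yes if the 4.4 definition applies |
| 9.3, adherence | Complete the program | Unclear when read alone |
| 4.3, adherence | One session plus 8-week visit | Yes |
| 4.4, completion of intervention phase | Randomized, one session, 8-week visit | Yes |
| 9.4.2, adherence | Not dropped out before the 8-week visit | Yes; non-adherent if below 75% of classes |
| 9.4.5 b, composite | Not dropped out of the study | Passes b, but must also meet 75% attendance (c) |

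**2. Size of the Aim 2 gap**

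Inputs from the plan: 36 women allocated 1:1, so 36/2 = 18 per arm if balanced (9.2, 6.3); expectation over 75% (9.4.3).

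Assumptions: 3 drop-outs per arm (3/18 = 16.7%, inside the 15-25% band that 9.4.2 calls acceptable), leaving n = 18 − 3 = 15 at the 8-week visit; s stoppers among them, from 0 to 4; all stoppers average below 3; about 85% of the others reach 3.

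With x successes, the rate without stoppers is x/(n − s) and the rate with them is x/n.

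| s | Stoppers excluded | Stoppers included | Gap (points) |
|---|---|---|---|
| 0 | 13/15 = 86.7% | 13/15 = 86.7% | 0 |
| 1 | 12/14 = 85.7% | 12/15 = 80.0% | 5.7 |
| 2 | 11/13 = 84.6% | 11/15 = 73.3% | 11.3 |
| 3 | 10/12 = 83.3% | 10/15 = 66.7% | 16.7 |
| 4 | 9/11 = 81.8% | 9/15 = 60.0% | 21.8 |

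With 2 or more stoppers, the choice of population decides which side of 75% the rate falls on.

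In general the gap is (s/n) × (success rate of the others − success rate of the stoppers). If 1 of 3 stoppers reaches a rating of 3, it is (3/15) × (83.3% − 33.3%) = 10.0 points, that is 10/12 = 83.3% against 11/15 = 73.3%. If stoppers do as well as the others, it is zero.

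**The case against.** The best defence is that the plan, read as a whole, already includes these women in Aim 2. The sentence after the Aim 2 rule in 9.3 keeps women who miss classes. Section 7 mostly uses discontinuing for interventions and withdrawing for the study, so early withdrawal could mean study withdrawal. Section 9.4.3 speaks of completing the program, and under 4.4 one session and the 8-week visit are enough. Section 9.4.4 also moves freely between completing the programs and reaching the 8-week timepoint.

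This shows that the Aim 2 text is ambiguous and that a bias is not demonstrated. It does not settle the reading. The rule in 9.3 names the program where 9.4.5 names the study. Missing classes is not the same as leaving the program. Section 4.4 defines completing the intervention phase, and neither 9.3 nor 9.4.3 points to it.

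A reader might infer that the adherence rates are inflated too, or are circular because only class completers are assessed for class attendance. The documents do not support that. Sections 4.3, 4.4 and 9.4.2 all rest on the 8-week visit and set no minimum attendance beyond one session (9.4.2 does not state even that). A stopper therefore stays in the denominator and counts against adherence. Section 9.3 is only worded inconsistently with them.

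**Conclusion.** The point holds for Aim 2 as a conditional risk. Applied literally, 9.3 can remove women whose 8-week self-efficacy data are scheduled and who may well be teaching failures. On the assumed counts the gap runs from 0 to about 22 points for 0 to 4 stoppers per arm. It shrinks if some stoppers reach a rating of 3. That stoppers rate lower is plausible, but nothing in the documents shows it, and the counts are illustrative.

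It would go too far to conclude that a program many women abandon could pass every component benchmark unnoticed. Under 4.3 and 9.4.2 low attendance by stoppers lowers the adherence rate. The composite is also unaffected: it is a count against 24 (two-thirds of 36), with its own attendance and self-efficacy criteria and no denominator taken from 9.3.

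**What to change.** - In 9.3 and 9.4.3, define the Aim 2 population as randomized women who attended at least one session and completed the 8-week visit, whether or not they stopped classes or home practice. This is the 4.3/4.4 population.
- Use the same wording for adherence in 9.3, and align 9.4.2 with it on the one-session condition. Count classes and practice hours after stopping as not completed.
- Report the number of stoppers per arm beside each rate.
- For observed competence, report how many women lack an 8-week consultant rating. Show the rate among those rated, and again with unrated stoppers counted as not competent. Ratings may be missing because 6.2.1 describes the consultant evaluating students while observing a class. The schedule in 1.3 lists the evaluation at 8 weeks, but the 8-week visit list in 8.1 does not.

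The cost is wording and a few extra table rows; no new self-efficacy data are needed. The Aim 2 percentages may come out slightly less favourable, and the competence rate may have to be shown as a range.
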